5.2. Number of Participants

For the target sample size of 8 evaluable participants each in mild, moderate and severe hepatic impairment groups, the maximum the number of evaluable participants in this study is 48 (assuming 24 matching participants with normal hepatic function for the 24 hepatically impaired participants).

Due to the potential difficulty in identifying eligible participants with severe hepatic impairment, the sponsor may stop the study prior to full enrollment in Part 2 provided that a minimum of 6 evaluable participants with severe hepatic impairment have been enrolled.

If participants prematurely discontinue the study, additional replacement participants may be recruited at the discretion of the Sponsor in consultation with the investigator.

5.3. Participant and Study Completion

A participant is considered to have completed the study if he/she has completed all phases of the study including the Follow-up Visit.

The end of the study is defined as the date of the last visit of the last participant in the study.

5.4. Scientific Rationale for Study Design

This study design is commonly used when evaluating the pharmacokinetics of a drug entity in participants with impaired hepatic function. It is based on recommendations given in the FDA Guidance for Industry, Pharmacokinetics in Patients with Impaired Hepatic Function: Study Design, Data Analysis, and Impact on Dosing and Labeling [DHHS, 2003].

Gepotidacin exhibits linear and time-independent pharmacokinetics, which indicates a single-dose study is adequate to achieve study objectives.

In the human ADME study (see report of study BTZ115774), total recovery of radioactivity was approximately 84% (31.2% in urine and 52.5% in feces) after oral administration. Radioactivity was eliminated in higher proportions in feces for oral doses, suggesting hepatic impairment could affect clearance of the parent compound. The absolute oral bioavailability was approximately 44%.

5.5. Dose Justification

The oxidative metabolism of gepotidacin is mediated primarily by cytochrome P450 enzyme 3A4 (CYP3A4). In a clinical drug-drug interaction study when itraconazole (inhibitor of both p-glycoprotein and CYP3A4) was co-administered with gepotidacin, a weak drug-drug interaction (40% increase in C_{max} and 50% increase in AUC[0-∞]) was observed (see GSK Document Number [2014N199850_00](#) Study ID BTZ117349). Therefore, the mean C_{max} and AUC following a single oral dose of gepotidacin 1500 mg are not expected to exceed those observed in healthy adult participants who received

gepotidacin 3000 mg (see GSK Document Number [2012N137722_00](#) Study ID BTZ114595).

6. STUDY POPULATION

Prospective approval of protocol deviations to recruitment and enrollment criteria, also known as protocol waivers or exemptions, is not permitted.

6.1. Inclusion Criteria

Participants are eligible to be included in the study only if all of the following criteria apply:

Age

1. Participant must be 18 to 80 years of age inclusive, at the time of signing the informed consent.

Type of Participant and Disease Characteristics

2. Healthy participants must be in clinically stable health as determined by the investigator based on medical history, clinical laboratory results (serum chemistry, hematology, urinalysis, and serology), vital sign measurements, 12-lead electrocardiogram (ECG) results, and physical examination findings.
3. Hepatically impaired participants must have chronic (>6 months), stable (no acute episodes of illness within the previous 1 month prior to screening due to deterioration in hepatic function) hepatic insufficiency with features of cirrhosis due to any etiology. Participants must also remain stable throughout the Screening period.
4. Hepatically impaired participants will be classified using the Child-Pugh classification system (see [Table 3](#)). Participants must have a Child-Pugh score of 5 to 6 (mild hepatic impairment), 7 to 9 (moderate hepatic impairment), or 10 to 15 (severe hepatic impairment) with known medical history of liver disease (with or without a known history of alcohol abuse) and previous confirmation of liver cirrhosis by liver biopsy or other medical imaging technique (including laparoscopy, computed tomography scan, magnetic resonance imaging, or ultrasonography) associated with unambiguous medical history. If imaging study or biopsy is not available, then the participant should have one of the following:
 - i. Physical findings such as hepatomegaly, ascites, palmar erythema, spider angiomas, abdominal venous collaterals, gynecomastia, or other physical manifestations of hepatic disease

OR

- ii. Laboratory findings: alanine aminotransferase (ALT) or aspartate aminotransferase elevation (> upper limit of normal [ULN]), alkaline phosphatase, or total bilirubin, or international normalized ratio (INR) elevation (>ULN) or an albumin value that is below the lower limit of normal laboratory reference range.

5. Participants with hepatic impairment may be taking medications which, in the opinion of the investigator, are believed to be therapeutic, and these medications should not interfere with the conduct of the study. Participants with hepatic impairment should be on stable regimen of chronic medications for at least 7 days prior to dosing until completion of the Follow-Up Visit.
6. Participants with hepatic impairment must have platelet counts $\geq 30,000 \times 10^9/L$ of blood and have not had any major bleeding episodes within the past 6 months.

Weight

7. Body weight ≥ 45 kg and BMI within the range 18.5 to 40 kg/m² (inclusive).

Sex

8. Male or female

a. Male participants:

A male participant must agree to use contraception as detailed in [Appendix 2](#) of this protocol from Day -1 until completion of the Follow-up Visit.

b. Female participants:

A female participant is eligible to participate if she is not pregnant (see [Appendix 2](#)), not breastfeeding, and at least one of the following conditions applies:

- i. Not a woman of childbearing potential (WOCBP) as defined in [Appendix 2](#)

OR

- ii. A WOCBP who agrees to follow the contraceptive guidance in [Appendix 2](#) from 30 days prior to study drug administration and until completion of the Follow-up Visit.

Informed Consent

9. Capable of giving signed informed consent as described in [Appendix 3](#) which includes compliance with the requirements and restrictions listed in the informed consent form (ICF) and in this protocol.

6.2. Exclusion Criteria

Participants are excluded from the study if any of the following criteria apply:

Medical Conditions

1. Participant has a clinically significant abnormality in past medical history or at the Screening physical examination (excluding hepatic insufficiency and other related medical conditions within the hepatically impaired populations which should be stable for at least 1 month before study drug administration) that in the investigator's opinion may place the participant at risk or interfere with outcome variables of the study. This includes, but is not limited to, history or current significant cardiac, renal, neurologic, gastrointestinal, respiratory, hematologic, or immunologic disease.

2. Participant has any surgical or medical condition (active or chronic) that may interfere with drug absorption, distribution, metabolism, or excretion of the study drug, or any other condition that may place the participant at risk, in the opinion of the investigator.
3. Female participant has a positive pregnancy test result or is lactating at Screening or upon admission to the clinic.
4. Participant has used a systemic antibiotic within 7 days of Screening.
5. Participant has a confirmed history of *Clostridium difficile* infection or a positive *C. difficile* toxin test within 2 months before Screening.
6. Participant has a history of drug and/or alcohol abuse within 6 months before Screening, as determined by the investigator, or participant has a positive drug screen at Screening or upon admission to the clinic. For participants with hepatic impairment, and a positive drug screen result related to the use of prescription medications is allowed per investigator review and approval, and tetrahydrocannabinol use is allowed per investigator review and approval.
7. History of sensitivity to any of the study drugs, components thereof, or a history of drug or other allergy that, in the opinion of the investigator or GSK medical monitor, contraindicates their participation.
8. History of sensitivity to heparin or heparin-induced thrombocytopenia (if the clinic uses heparin to maintain intravenous cannula patency).

Prior/Concomitant Therapy

9. Participant has used medications known to affect the elimination of serum creatinine (e.g., trimethoprim or cimetidine) or competitors of renal tubular secretion (e.g., probenecid) within 30 days before dosing.
10. Participants must abstain from taking prescription or nonprescription drugs (including vitamins and dietary or herbal supplements), unless specified in Section 7.7.1, within 7 days (or 14 days if the drug is a potential strong enzyme inducer) or 5 half-lives (whichever is longer) prior to study drug administration until completion of the Follow-Up Visit, unless, in the opinion of the investigator and Sponsor, the medication will not interfere with the study. Any exceptions (including participants with hepatic impairment that will be on medications during the study) will be discussed with the sponsor or medical monitor on a case-by-case basis and the reasons will be documented.

Prior/Concurrent Clinical Study Experience

11. Previous exposure to gepotidacin within 12 months prior to study drug administration.
12. The participant has participated in a clinical trial and has received an investigational product within the following time period prior to study drug administration in the current study: 30 days, 5 half-lives, or twice the duration of the biological effect of the investigational product (whichever is longer).

Diagnostic Assessments

13. Participant with normal hepatic function has presence of hepatitis B surface antigen or positive hepatitis C antibody test result at Screening or within 3 months prior to study drug administration. Participant with hepatic impairment has evidence of recent, acute infection with hepatitis B and/or hepatitis C within preceding 6 months. Hepatically impaired participants with chronic hepatitis B or C (duration >6 months) are eligible for enrolment.
14. A positive test for human immunodeficiency virus antibody.
15. Participant must be able to abstain from alcohol and limit use of nicotine and/or nicotine-containing products (up to 5 cigarettes/day is acceptable for participants with hepatic impairment) for 24 hours before the start of dosing until after collection of the final PK sample. A positive alcohol or cotinine test is not exclusionary for participants with hepatic impairment.
16. Participant has clinically significant abnormal findings in serum chemistry, hematology, or urinalysis results obtained at Screening or Day -1, other than those associated with underlying hepatic conditions or other stable medical conditions consistent with the disease process in participants with hepatic impairment.
17. Participant with normal hepatic function has a baseline corrected QT interval using the Fridericia formula (QTcF) of >450 milliseconds (msec) and participant with hepatic impairment has a baseline QTcF of >480 msec.

Other Exclusions

18. Donation of blood in excess of 500 mL within 12 weeks prior to dosing or participation in the study would result in donation of blood or blood products in excess of 500 mL within a 56-day period.
19. Participant is unable to comply with all study procedures, in the opinion of the investigator.
20. The participant should not participate in the study, in the opinion of the investigator or Sponsor.

Supplemental Exclusion Criteria for Hepatically Impaired Participants

21. Participants with a pre-existing condition (except hepatic impairment) interfering with normal GI anatomy or motility that could interfere with the absorption, metabolism, and/or excretion of the study drugs. Participants with a history of inflammatory bowel disease should be excluded. Participants with a history of peptic ulceration or pancreatitis within the preceding 6 months of screening should be excluded.
22. Participants with any previous GI surgery (except appendectomy or gall bladder removal >3 months prior to Screening) may be enrolled in this study only if, in the opinion of the investigator and the medical monitor, it is not expected to interfere with the study procedures or to pose an additional safety risk to the participant.

23. Participants receiving lactulose who are medically unable to halt lactulose administration from 8 hours before dosing with study drug to 4 hours after dosing with study drug.
24. Participants with clinically active severe encephalopathy (grade 3 or 4 as defined in [Table 3](#)) as judged by the investigator or significant central nervous system disease (e.g., dementia or seizures) which the investigator considers will interfere with the informed consent, conduct, completion, or results of this trial or constitutes an unacceptable risk to the participant. Participants with a prior history of severe encephalopathy who are currently treated for this condition will receive the appropriate score for encephalopathy.
25. Participants with estimated creatinine clearance (Clcr) ≤ 50 mL/min (calculated by the Cockcroft-Gault Formula). If the result calculated by Cockcroft-Gault is between 40 and 50 mL/min, then the site may complete a 24-hour urine collection to more specifically calculate the Clcr. A Clcr value ≤ 50 mL/min via 24-hour urine collection is also exclusionary.
26. History of gastric or esophageal variceal bleeding within the past 6 months and for which varices have not been adequately treated with medication and/or surgical procedures.
27. Participants with electrolyte imbalance whose serum sodium levels are ≤ 125 mmol/L; potassium levels are ≤ 2.5 mmol/L; or calcium levels are ≤ 6.1 mmol/L.
28. Presence of hepatopulmonary or hepatorenal syndrome.
29. Primary cholestatic liver diseases.
30. History of liver transplantation or participants in the severe hepatic impairment group that are expecting a liver transplant during the study participation period.
31. Participants with signs of active bacterial infection (including active spontaneous bacterial peritonitis).
32. Participants with transjugular intrahepatic portosystemic shunt placement within the past 3 months.
33. Participants with unstable cardiac function or participants with hypertension whose blood pressure that is not well controlled (based on the investigator's discretion).
34. Diabetic participants whose diabetes that is not controlled (based on the investigator's discretion).

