12.10. Appendix 10: DMID Adult Toxicity Tables for AE Assessment

ESTIMATING SEVERITY GRADE: For abnormalities NOT found elsewhere in the Toxicity Tables, use the scale below to estimate grade of severity:

GRADE 1	Mild	Transient or mild discomfort (<48 hours); no medical intervention/therapy required
GRADE 2	Moderate	Mild to moderate limitation in activity – some assistance may be needed; no or minimal medical intervention/therapy required
GRADE 3	Severe	Marked limitation in activity, some assistance usually required; medical intervention/therapy required, hospitalizations possible
GRADE 4	Life-threatening	Extreme limitation in activity, significant assistance required; significant medical intervention/therapy required, hospitalization or hospice care probable

SERIOUS OR LIFE-THREATENING AEs: ANY clinical event deemed by the investigator to be serious or life-threatening should be considered a grade 4 event. Clinical events considered to be serious or life-threatening include, but are not limited to: seizures, coma, tetany, diabetic ketoacidosis, disseminated intravascular coagulation, diffuse petechiae, paralysis, acute psychosis, and severe depression.

COMMENTS REGARDING THE USE OF THESE TABLES

- Standardized and commonly used toxicity tables (Division of AIDS, National Cancer Institute’s Common Toxicity Criteria, and World Health Organization) have been adapted for use by the NIAID DMID and modified to better meet the needs of participants in DMID trials.
- For parameters not included in the following Toxicity Tables, sites should refer to the “Guide for Estimating Severity Grade” located above.
- Criteria are generally grouped by body system.
- Some protocols may have additional protocol specific grading criteria, which will supersede the use of these tables for specified criteria.

HEMATOLOGY				
	Grade 1	Grade 2	Grade 3	Grade 4
Hemoglobin	9.5 to 10.5 gm/dL	8.0 to 9.4 gm/dL	6.5 to 7.9 gm/dL	<6.5 gm/dL
Absolute Neutrophil Count	1000 to 1500 /mm ³	750 to 999 /mm ³	500 to 749 /mm ³	<500 /mm ³
Platelets	75,000 to 99,999 /mm ³	50,000 to 74,999 /mm ³	20,000 to 49,999 /mm ³	<20,000 /mm ³
White Blood Cells	11,000 to 13,000 /mm ³	13,000 to 15,000 /mm ³	15,000 to 30,000 /mm ³	>30,000 or <1000 /mm ³
% Polymorphonuclear Leukocytes + Band Cells	>80%	90 to 95%	>95%	N/A

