Abnormal Fibrinogen	Low: 100 to 200 mg/dL High: 400 to 600 mg/dL	Low: <100 mg/dL High: >600 mg/dL	Low: <50 mg/dL High: N/A	Fibrinogen associated with gross bleeding or with disseminated coagulation
Fibrin Split Product	20 to 40 mcg/mL	41 to 50 mcg/mL	51 to 60 mcg/dL	>60 mcg/dL
Prothrombin Time (PT)	1.01 to 1.25 × ULN	1.26 to 1.5 × ULN	1.51 to 3.0 × ULN	>3 × ULN
Activated Partial Thromboplastin (APTT)	1.01 to 1.66 × ULN	1.67 to 2.33 × ULN	2.34 to 3 × ULN	>3 × ULN
Methemoglobin	5.0 to 9.9%	10.0 to 14.9%	15.0 to 19.9%	>20%

N/A = not applicable; ULN = upper limit of normal.

CHEMISTRIES				
	Grade 1	Grade 2	Grade 3	Grade 4
Hyponatremia	130 to 135 mEq/L	123 to 129 mEq/L	116 to 122 mEq/L	<116 mEq/L or abnormal sodium with mental status changes or seizures
Hypernatremia	146 to 150 mEq/L	151 to 157 mEq/L	158 to 165 mEq/L	>165 mEq/L or abnormal sodium with mental status changes or seizures
Hypokalemia	3.0 to 3.4 mEq/L	2.5 to 2.9 mEq/L	2.0 to 2.4 mEq/L or intensive replacement therapy of hospitalization required	<2.0 mEq/L or abnormal potassium with paresis, ileus, or life-threatening arrhythmia
Hyperkalemia	5.6 to 6.0 mEq/L	6.1 to 6.5 mEq/L	6.6 to 7.0 mEq/L	>7.0 mEq/L or abnormal potassium with life-threatening arrhythmia
Hypoglycemia	55 to 64 mg/dL	40 to 54 mg/dL	30 to 39 mg/dL	<30 mg/dL or abnormal glucose with mental status changes or coma
Hyperglycemia (nonfasting and no prior diabetes)	116 to 160 mg/dL	161 to 250 mg/dL	251 to 500 mg/dL	>500 mg/dL or abnormal glucose with ketoacidosis or seizures
Hypocalcemia (corrected for albumin)	8.4 to 7.8 mg/dL	7.7 to 7.0 mg/dL	6.9 to 6.1 mg/dL	<6.1 mg/dL or abnormal calcium with life-threatening arrhythmia or tetany
Hypercalcemia (corrected for albumin)	10.6 to 11.5 mg/dL	11.6 to 12.5 mg/dL	12.6 to 13.5 mg/dL	>13.5 mg/dL or abnormal calcium with life-threatening arrhythmia
Hypomagnesemia	1.4 to 1.2 mEq/L	1.1 to 0.9 mEq/L	0.8 to 0.6 mEq/L	<0.6 mEq/L or abnormal magnesium with life-threatening arrhythmia
Hypophosphatemia	2.0 to 2.4 mg/dL	1.5 to 1.9 mg/dL or replacement Rx required	1.0 to 1.4 mg/dL intensive therapy or hospitalization required	<1.0 mg/dL or abnormal phosphate with life-threatening arrhythmia
Hyperbilirubinemia (when accompanied by any increase in other liver function test)	1.1 to <1.25 × ULN	1.25 to <1.5 × ULN	1.5 to 1.75 × ULN	>1.75 × ULN

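### Platelet and calcium eligibility limits for hepatically impaired participants pair numbers with units that cannot work as printed

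*Protocol*

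**What the plan says.** Inclusion criterion 6 (Protocol 6.1) reads: "Participants with hepatic impairment must have platelet counts $\geq 30,000 \times 10^9/L$ of blood". The same criterion also bars recent major bleeding.

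Exclusion criterion 27 (Protocol 6.2, supplemental criteria for hepatically impaired participants) begins "Participants with electrolyte imbalance whose serum sodium levels are ≤ 125 mmol/L". It goes on to a potassium limit of 2.5 mmol/L and ends "or calcium levels are ≤ 6.1 mmol/L". All three limits take the same direction: at or below the figure is exclusionary.

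Appendix 10, the toxicity table for grading adverse events, shows the scales the protocol uses elsewhere:

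- **Platelets** are graded as whole counts per mm³. Grade 1 is "75,000 to 99,999 /mm ³".
- **Calcium** is graded in mg/dL after albumin correction. Hypocalcemia starts at 8.4 and reaches Grade 4 below 6.1. Hypercalcemia starts at 10.6, and its Grade 4 entry is ">13.5 mg/dL or abnormal calcium" with qualifying features.
- **Sodium**: Grade 2 hyponatremia is "123 to 129 mEq/L".
- **Potassium**: Grade 2 hypokalemia is "2.5 to 2.9 mEq/L".

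Protocol Sections 6 and 9 rule out waivers. Neither the protocol nor the SAP states either limit a second time.

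**The concern.** An eligibility limit has to separate those who may enter from those who may not. These two appear unable to do so. The calcium limit, written as a floor, sits far above the protocol's own ceiling. The platelet limit joins a number in the style of a count per mm³ to a 10^9/L multiplier, which scales it twice.

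These are the only numeric platelet and calcium screens for participants with cirrhosis. The general laboratory exclusion (criterion 16) exempts abnormalities tied to the liver condition, so for those the plan falls back on judgement, as in criterion 20.

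In a multi-center study, sites that each supply their own reading may reach different eligibility decisions. Each such decision could be a formal deviation, because waivers are not allowed. SAP 4.1 summarises and lists inclusion/exclusion deviations from what sites enter on the eCRF page, so the report would reflect each site's reading and not a common written rule.

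**Working it through.** The protocol gives no derivation for either limit, so there is no figure to reproduce. The check converts each printed limit to the Appendix 10 units and compares. Appendix 10 is an adverse-event grading table and not a competing eligibility rule; it serves here only as a scale.

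**Calcium**

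- Input: 6.1 mmol/L (exclusion 27).
- Assumption, not in the documents: atomic mass of calcium 40.08, so 1 mmol/L = 40.08 / 10 = 4.008 mg/dL.
- 6.1 × 4.008 = 24.45 mg/dL. With atomic mass from 40.0 to 40.1 the result is 24.40 to 24.46.
- Against Grade 4 hypercalcemia: 24.45 / 13.5 = 1.81.
- Against the start of Grade 1 hypercalcemia: 24.45 / 10.6 = 2.31.

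| Appendix 10 point | mg/dL | mmol/L (÷ 4.008) |
|---|---|---|
| Hypocalcemia Grade 1 begins | 8.4 | 2.10 |
| Hypercalcemia Grade 1 begins | 10.6 | 2.64 |
| Hypercalcemia Grade 4 lies above | 13.5 | 3.37 |
| Exclusion 27 as printed | 24.45 | 6.1 |

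The whole ungraded range, about 2.10 to 2.64 mmol/L, lies below the printed limit. So do all low values and Grade 4 high values up to about 24.4 mg/dL.

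Reading the figure as mEq/L does not rescue it. Calcium is divalent, so 6.1 mEq/L = 6.1 / 2 × 4.008 = 12.2 mg/dL, still above 10.6.

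**Sodium and potassium, same sentence**

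Both ions are monovalent, so mmol/L equals mEq/L. Sodium 125 falls within 123 to 129 and potassium 2.5 within 2.5 to 2.9, both Grade 2 low bands. These two behave as low limits, so the fault is confined to calcium.

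**Platelets**

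- Input: 30,000 × 10^9/L (inclusion 6).
- 1 L = 10^6 mm³, so 30,000 × 10^9 / 10^6 = 30,000,000/mm³.
- Against the top of Grade 1: 30,000,000 / 99,999 = 300.
- Sensitivity to the exponent: with 10^6 in place of 10^9, the figure would be 30,000/mm³ and the platelet problem would disappear.

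**Same digits elsewhere in Appendix 10**

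The figure 6.1 is the boundary between Grade 3 and Grade 4 hypocalcemia, in mg/dL. The figure 30,000, read per mm³, lies in the Grade 3 platelet band (20,000 to 49,999). These matches make a unit slip likely. They do not establish which limits were intended.

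**The case against.** The strongest objection concerns platelets. The text was converted from PDF, and a 6 misread as a 9 in the exponent would produce the whole problem. That stands as a caveat: the platelet half depends on the source file. It does not touch calcium, which is plain text.

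The platelet row of Appendix 10 grades only low counts, so 300 times its top figure does not by itself prove that nobody qualifies. This is also fair. That conclusion needs the further assumption that no participant has a count near 30 million/mm³, which is hardly contentious.

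The opening words of criterion 27 may confine it to participants already judged to have an imbalance. Even so, the printed calcium figure could not tell low calcium from normal or high.

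Other criteria cover related risks: recent major bleeding (inclusion 6), variceal bleeding (exclusion 26), QTcF (exclusion 17), unstable cardiac function (exclusion 33) and any condition that places the participant at risk (exclusion 2). They narrow the safety gap, but none supplies a calcium or platelet limit.

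Finally, sites may well spot the slip and read it alike, and the laboratory manual, reference manual and eCRF are not available to show otherwise. The operational effect is therefore unknown. A common guess is still not a written rule.

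**Conclusion.** The concern holds. As printed, the calcium limit is about 24.4 mg/dL, 1.8 times the Grade 4 hypercalcemia cut-off and 2.3 times the point where hypercalcemia grading begins. This rests only on the atomic mass of calcium, and the range tried does not alter the conclusion. The platelet limit is 30,000,000/mm³, 300 times the top of the Grade 1 band, provided the printed exponent is confirmed.

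Both criteria apply to Groups A, B and C: 3 × 8 = 24 evaluable participants at most, fewer if optional Group A is not enrolled or Group C stops at 6. The likely result is unclear or inconsistent eligibility decisions and possible formal deviations. Zero enrolment, universal deviations and loss of PK data are not claimed. The criteria should be corrected, but the design and analysis are not in question.

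**What to change.** Amend inclusion criterion 6 and exclusion criterion 27 so that each number agrees with its unit. The sponsor must state the intended limits, after checking the platelet exponent in the source file. No particular limit is proposed here.

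Two clarifications belong in the same amendment:

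- **Albumin correction.** State whether the calcium limit applies to albumin-corrected calcium. Appendix 10 labels its row "Hypocalcemia (corrected for albumin"), criterion 27 is silent, and albumin is itself a Child-Pugh item. The gap found above is too wide for correction to explain, but the answer will matter once the limit is workable.
- **Scope.** State whether criterion 27 applies to every impaired participant or only to those already judged to have an imbalance.

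It would help to express both limits in the Appendix 10 units, or to give the conversion, and to use the same units in any central laboratory eligibility flags.

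The cost is a short amendment or clarification to two criteria and a sponsor decision on albumin correction. Design, sample size and analysis are unchanged.
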